- *Specific Aim 2:* To determine the adherence of patients and health care team to the procedures included in the study protocol (scheduled appointments, surveillance and transfusion strategies).
- *Specific Aim 3:* To determine the increase in hemoglobin levels and reticulocyte count following a

short-course of EPO plus supplemental IV iron vs. standard of care management in matched patients scheduled for CABG, valve, or CABG/valve surgery.

- *Specific Aim 4:* To assess differences in the proportion of patients receiving erythrocyte transfusions and number of blood products utilized (RBC, platelets and plasma) in the peri- and post-operative periods for those receiving a short-course of EPO plus supplemental IV iron vs. standard of care management in matched patients scheduled for CABG, valve, or CABG/valve surgery.
- *Specific Aim 5:* To determine the frequency and intensity of pre-defined clinical outcomes (mortality, major cardiac, renal, neurological events [associated with anemia] and infection) in those receiving a short-course of EPO plus supplemental IV iron vs. standard of care management in matched patients scheduled for CABG, valve, or CABG/valve surgery.

II. BACKGROUND:

Active preoperative anemia management is *not* currently the standard of care at our institution. Cost associated with erythrocyte transfusions at UT Southwestern University Hospitals exceeds \$20M dollars annually. This figure does not include costs associated with treatment of known complications of red blood cells transfusions (renal insufficiency, respiratory failure, infection and prolonged length of stay, etc).¹⁹⁻²⁰ Fifty percent (50%) of our cardiac surgical population suffers from preoperative anemia and seventy-nine (79%) of these patients will receive one or more erythrocyte transfusions. In contrast, the incidence of erythrocyte transfusion was only 35% in those *without* preoperative anemia in CY2011-12.

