surveillance strategies. We define successful adherence as adhering to dosing in $\geq 90\%$ of patients for $\geq 90\%$ of the doses deemed appropriate by the surveillance strategy. Secondary outcomes will include:

- 1) changes in hemoglobin levels and reticulocyte counts within the two groups from baseline to the day of surgery (preop to POD#0) and POD#5;
- 2) proportion of patients receiving erythrocyte transfusions and number of blood products (RBC, platelets and plasma) utilized;
- 3) incidence of pre-defined clinical events (mortality, major cardiac, renal, neurological events [associated with anemia] and infection) in each of the study groups.

[figure not shown]
These events will include myocardial infarction, prolonged low-output state, stroke, encephalopathy, duration of mechanical ventilation, renal insufficiency, and mortality and dialysis dependence at 30 days or discharge. Data from this feasibility study will be used for the power analysis and design of the larger RCT.

Clinical events will be defined using the following criteria: Society of Thoracic Surgery (STS)⁴² for stroke/transient ischemic attack (TIA), coma/encephalopathy, myocardial infarction (MI), prolonged ventilation, reoperation for bleeding or graft occlusion/revision, postoperative venous thrombosis, thromboembolic event, deep venous thrombosis and pulmonary embolism; RIFLE⁴³⁻⁴⁴ for acute renal injury (AKI), National Healthcare Safety Network (NHSN)⁴⁵ for surgical site infections (SSI); Surgenor SD et al.⁴⁶ for low output heart failure (LOHF); any life-threatening events (i.e., subject was at substantial risk of dying at the time of the adverse event) and in-hospital or 30-day mortality based on observation. Outcome data will be collected via contact with primary physician, public record review or by a follow-up telephone call by the research nurse.

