Adverse events are events that involve physiological, social, or psychological harm to subjects or risks of harm to additional subjects or others. AEs include expected and unexpected harmful effects, and unexpected risks of an interaction or an intervention. AEs may be caused by: the test article or test procedure, other aspects of the interaction or intervention, the subject's underlying condition, or the subject's concurrent standard treatment. AEs may be definitely related, probably related, possibly related, unlikely to be related, or definitely not related *to the research*.

B. Method of Identifying, Recording, Monitoring and Reporting Adverse Events:

We will report all adverse events and other reportable incidences and occurrences to the IRB per reporting guidelines. Any adverse event will be documented of that event including a description, subject number, date, outcome, and follow-up.

C. Safety Endpoints:

The primary safety endpoints of the study are the incidence of adverse events associated with the use of the study medications. These include: hypersensitivity (e.g. pruritis, rash, and urticaria), hypertension, hypotension, bleeding, nausea, vomiting, injection site pain, deep venous thrombosis or other thrombotic complications. Surveillance for these adverse events will be conducted by direct observation (during drug administration), daily bedside visits by the research nurse for the first 7 postoperative days, review of the patient's medical record and listing any of these complication in the Society of Thoracic Surgery (STS) database. The definition of a stroke, myocardial infarction (MI), mesenteric artery occlusion or peripheral vascular event will be based on STS criteria.³⁷ Any event resulting in death from time of initial drug administration to hospital discharge will be recorded.

XII. PROCEDURES TO MAINTAIN CONFIDENTIALITY

We will collect data from lab tests and EPIC, the electronic medical record.

Raw data: We will remove personal identifying information of the patients from the raw data and replace them with coded IDs before data processing and analysis. Any materials containing personal identifying information will be stored in a locked cabinet in the principal investigator's office. After data entry, any materials containing personal identifying information will be promptly and securely returned to the principal investigator. Any materials with personal identifying information on them will be shredded before discard.

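### The between-group event outcome does not clearly include venous or graft thrombosis, and no passage commits to counting these events in the matched controls

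*Combined protocol and SAP*

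**What the plan says.** Specific Aim 5 compares treated with matched patients on mortality, major cardiac and renal events, and "neurological events [associated with anemia] and infection". Secondary outcome 3 in Section III (Clinical Outcomes) repeats this as the "incidence of pre-defined clinical events (mortality, major cardiac, renal, neurological events [associated with anemia] and infection) in each of the study groups".

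The sentence after outcome 3 gives the content: "These events will include myocardial infarction, prolonged low-output state, stroke, encephalopathy, duration of mechanical ventilation, renal insufficiency, and mortality and dialysis dependence", the last two at 30 days or discharge. The following paragraph, under the same heading, says how clinical events are to be defined. Among those given STS definitions are "reoperation for bleeding or graft occlusion/revision, postoperative venous thrombosis, thromboembolic event, deep venous thrombosis and pulmonary embolism".

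Section XI.C sets the primary safety endpoints as adverse events linked to use of the study medications, including "deep venous thrombosis or other thrombotic complications". It finds them by direct observation during dosing, daily research-nurse visits for the first 7 postoperative days, the medical record and the STS database.

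The Section III summary plans 25 treated patients and 25 matched controls, and gives the STS database as the source of control data. The Biostatistics section calls the analysis mainly descriptive, centers it on confidence intervals and reports no power calculation.

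**The concern.** The protocol treats thrombosis as a leading risk of EPO. Section III counts it among the most common serious adverse effects and builds the dosing surveillance strategy around it. Section X refers to increased perioperative thrombotic risk. One would expect thrombotic events to be tabulated in both groups, yet the outcome that is stated by group does not name them, and the section that does name them speaks only of events tied to the drugs.

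Two things are at stake. First, the data are meant to guide a larger randomized trial. A thrombotic count in treated patients, with no count from matched patients beside it, gives that trial no background rate. Second, if the two groups are compared as the plan stands, events are sought more actively in treated patients than in controls, so a raw difference would mix drug effect with detection.

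The bracketed reference to anemia adds uncertainty. It follows the neurological events, and the text does not say whether it also covers cardiac and renal events. It could be used to set aside a stroke on the ground that its presumed cause was not anemia.

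**Working it through.** The plan gives no figure to reproduce on this point, so the main check is to set the passages side by side.

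| Place | Venous or graft thrombosis named? | Patients covered |
|---|---|---|
| Specific Aim 5 | No | Treated vs matched |
| Section III summary | No | All treated participants |
| Secondary outcome 3 | No | Each study group |
| Event list after outcome 3 | No | Not stated |
| Definitions paragraph, same heading | Yes | Not stated |
| Section XI.C | Yes | Tied to study medications |
| Biostatistics | No event outcome named | No safety comparison specified |

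Where thrombosis is named, the control group is not; where the control group is named, thrombosis is not. No passage joins the two.

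*Capture.* Of the four sources in Section XI.C, two (observation during dosing and the study nurse's visits) can apply only to enrolled, treated patients. Controls are drawn from the registry. The windows differ too: Section XI.C records deaths from first drug administration, a starting point that controls do not have.

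*Is a treated-group event plausible?* Section X places DVT among reactions seen in over 5% of EPO-treated perioperative patients. Assume a rate of exactly 5% and independent patients:

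- Expected cases: 25 × 0.05 = 1.25.
- P(at least one in 25) = 1 − 0.95^25 = 1 − 0.277 = 0.723, or 72%.

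At other assumed rates the same formula gives 22% (rate 1%), 40% (2%) and 93% (10%). These figures show only that an event may well occur. They do not measure bias in any comparison.

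*What could 25 per group show?* For no events in 25, the exact two-sided 95% upper limit is 1 − 0.025^(1/25) = 13.7%. Fisher's exact test at 0.05, taken as two-sided because the plan does not say, needs 6/25 against 0/25 to reach significance (p = 0.022); 5/25 against 0/25 gives p = 0.0502. Its exact power is 0.1% for assumed rates of 5% vs 1% or 5% vs 2%, and 2.3% for 10% vs 2%.

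**The case against.** The strongest reply is that the plan already includes these events. Outcome 3 counts pre-defined clinical events in each group, and the definitions paragraph under the same heading says how clinical events are defined and lists thrombosis among them. On that reading, thrombosis is part of outcome 3. The event list is plainly not exhaustive: it also omits infection, which outcome 3 names and the definitions paragraph defines. A figure that is not shown in the available text also sits between outcome 3 and the list, so completeness cannot be judged from the list alone. Much of this stands. Inclusion may well have been intended, but a definition is not a commitment to tabulate by group.

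A second reply is that Section XI.C names the STS database, which is also the control source, so nothing bars counting thrombosis in controls. Section VIII mentions medical records as well, without saying for which group. That is fair, and it makes the remedy easy. It does not supply the missing statement or equalize capture.

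A reader might go further and infer that the comparison leaves out EPO's main risk and so can only lean toward benefit. The documents do not support that. Myocardial infarction, stroke and death are in the list. Section III cites EPO labeling for increased risk of all three at higher hemoglobin targets in patients with chronic kidney disease, and Section X says EPO may raise cardiovascular risk, including death. Nor do the documents set up any adjudication of strokes or infarctions by cause; the bracket is unclear rather than an exclusion rule.

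Finally, Section X warns that trial adverse reaction rates may not apply here, and 25 per group cannot test a difference. Both points stand. They limit what a comparison can show, but reporting both groups with intervals still fits the plan's descriptive aim.

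**Conclusion.** The point holds as a gap in wording and reporting. Aim 5 and secondary outcome 3 do not clearly include venous or graft thrombosis, the event list and the definitions paragraph do not match, and no passage commits to a thrombotic count in the controls. As written, any comparison would also rest on unequal capture.

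The plan does not lack thrombotic outcomes: they are defined, and they are primary safety endpoints. No planned number changes. The 72% rests on an assumed 5% DVT rate and serves only as illustration. With 25 per group, even zero events leaves an upper limit of 13.7%, so the gain is a properly described pair of counts for planning the later trial, not a test. The conclusion rests on the text available, without the figure that is not shown.

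**What to change.** 1. In Aim 5 and secondary outcome 3, add a thrombotic category reported in both groups under the STS definitions already given: venous thrombosis, DVT, pulmonary embolism, other thromboembolism, and reoperation for graft occlusion or revision. Bring the event list into line with the definitions paragraph.
2. Delete the bracketed anemia qualifier, or state that all STS-defined strokes and myocardial infarctions count whatever their presumed cause.
3. Report the count in each group with an exact confidence interval.
4. For the between-group comparison, use STS-coded events over the same window in both groups. Report events found only by direct observation or bedside surveillance, and any between first dose and surgery that fall outside that window, separately for the treated group.

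The cost is a change of wording: the definitions and the registry are already in the plan, and patient management is unaffected. The downside is that counts will be small, intervals wide and the comparison descriptive only. Events that the STS database does not code will drop out of the between-group comparison, which is why the treated-group surveillance findings should still be shown in full.

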Anemic patients scheduled to undergo CABG, valve, or CABG/valve surgeries will be considered for the study. Patients who fulfill all the inclusion/exclusion criteria will be asked to participate in the study. The proportion of screen failures and eligible patients who refuse to participate will be recorded using a screen failure log. Patients who agree to be in the study and sign an informed consent form will be sequentially enrolled into the treatment group. The treatment group will receive up to three doses of EPO 300U/kg. The first dose of study medication will be administered up to 28 days before the day of surgery and the second will be administered 1-7 days before the day of surgery. These first two doses will be given at least 7 days apart. A third dose may be administered two to four days following surgery. All 3 doses will be administered subcutaneously and per surveillance strategy guidelines. In addition, supplementation

with IV iron (feraheme; 510mg delivered per IV infusion over a minimum of 15 minutes) will be given following the first two preoperative doses of EPO.

Differences in hemoglobin levels and reticulocyte counts from baseline to the day of surgery (preop to POD#0) and postoperative day five (POD#5), proportion of patients receiving erythrocyte transfusions and number of blood products (RBC, platelets and plasma) utilized and pre-defined clinical events (mortality, major cardiac, renal, neurological events [associated with anemia] and infection) will be assessed in all treated participants. Each patient will be enrolled in the study up to 28 days before the day of surgery and for up to 30 days following the day of surgery. This feasibility propensity-matched study will sequentially enroll 23 more treatment subjects to total 25. The propensity-matching control group will be comprised of 25 total “like” patients for comparison. The source of the data for the control group will be the Society of Thoracic Surgery (STS) Database, an institutional registry.

Study medications:

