1. The subject must be between the age of 18 and 80 years old.
2. The subject must be diagnosed with preoperative anemia, defined as hemoglobin <13.0g/dL.
3. The subject must be scheduled for elective cardiac surgery (CABG, valve, or CABG/valve), including both first time and repeat procedures.
4. Female subjects of child bearing potential must have a documented negative pregnancy test within 7 days prior to the procedure.

5. The subject must sign a written informed consent prior to the procedure, using a form that is approved by the UT Southwestern Institutional Review Board.
6. The subject must agree to be compliant and return for all follow-up visits.

VII. CRITERIA FOR EXCLUSION OF SUBJECTS:

The subjects will be excluded if they meet any one of the following criteria:

1. Uncontrolled hypertension (defined as systolic pressure greater than 180mmHg, diastolic pressure greater than 100mmHg, not adequately controlled by anti-hypertensive therapy at the time of procedure).
2. Current renal failure on dialysis or serum creatinine [Cr]>3.0mg/dL. ¹
3. Unstable angina (defined by chest pain and ECG changes indicating ischemia at rest).
4. Thromboembolism within the past year.
5. Current active primary or metastatic malignancy or history of myeloid malignancy.
6. Seizures within the past year.
7. History of stroke within the last 6 months.
8. Patients who have platelet count lower than 50,000/mm³ or coagulation abnormality.
9. Sepsis or bacteremia defined by positive blood culture.
10. Patients who have known hypersensitivity to EPO or any of its components.
11. Patients who have known hypersensitivity to Feraheme or any of its components.
12. Patients who refuse blood transfusion, (i.e. Jehovah's Witnesses).
13. Pregnant or breast feeding.
14. Patients who are unable to provide informed consent or who has inability to understand or cooperate with study procedure.

VIII. SOURCES OF RESEARCH MATERIAL

Data will be obtained from the patient's medical records EPIC and the Society of Thoracic Surgery (STS) database entries. Laboratory tests for reticulocyte count and additional serum ferritin, cardiac biomarkers, serum creatinine, thromboelastographic and liver transaminase measurements will be obtained specifically for research purposes. Other tests conducted (e.g. hemoglobin concentration, creatinine, EKG) will be part of standard of care (see Table 1 for details regarding standard of care and for research only).

IX. RECRUITMENT METHODS AND CONSENTING PROCESS

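### The plan does not ensure that kidney injury, surgical-site infection and low-output failure are found from the same source and by the same rule in treated patients and registry controls, so the Aim 5 rate differences may be biased in either direction.

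*Combined protocol and SAP*

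**What the plan says.** **Definitions.** Section III, Clinical Outcomes, names a criterion for each type of event. STS definitions are used "for stroke/transient ischemic attack (TIA), coma/encephalopathy, myocardial infarction (MI), prolonged ventilation, reoperation for bleeding or graft occlusion/revision", and also for venous thrombosis and thromboembolic events. RIFLE is used "for acute renal injury (AKI), National Healthcare Safety Network (NHSN" for surgical-site infection, and the criteria of a cited cohort study "for low output heart failure (LOHF". On the protocol's own list, the last three are not STS definitions.

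**Control data.** Section III, Research Design and Methods: "The source of the data for the control group will be the Society of Thoracic Surgery (STS) Database, an institutional registry". On size: "The propensity-matching control group will be comprised of 25 total “like” patients for comparison"; on the treated side the study "will sequentially enroll 23 more treatment subjects to total 25".

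**Use of the events.** Specific Aim 5 is "To determine the frequency and intensity of pre-defined clinical outcomes (mortality, major cardiac, renal, neurological events [associated with anemia] and infection", compared between treated patients and matched controls. The third secondary outcome is the incidence of these events in each group. Clinical Outcomes says the data will feed the power analysis and design of the larger trial.

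**Other sources.** Section VIII: "Data will be obtained from the patient's medical records EPIC and the Society of Thoracic Surgery (STS) database entries". Table 1 marks creatinine as standard of care at every time point (standard of care or research at POD14). Clinical Outcomes has outcome data collected through the primary physician, public records or a telephone call from the research nurse. Section XI.C adds daily research-nurse visits for the first seven postoperative days as surveillance for adverse events of the study drugs. None of these statements mentions the registry controls.

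**The concern.** A between-group difference in an event rate means something only if the event is counted in the same way in both groups. For the STS-defined events, a registry control and a treated patient can at least share a definition. For kidney injury, surgical-site infection and low-output failure, the chosen criterion is not the STS one, and the only source assigned to controls is the STS registry. Someone carrying out the plan could classify treated patients by RIFLE, NHSN and the low-output criteria from study data, take whatever the registry codes for controls, and still be following the text.

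Propensity matching does not help here: it balances baseline covariates, not the way outcomes are counted. A confidence interval does not reveal the problem either, because it shows sampling error and not a shift in the quantity being estimated. Renal events and infection are named Aim 5 outcomes. A false harm signal, or a masked real one, could be carried into the design of the randomized trial.

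**Working it through.** **1. Sources and rules side by side.** The definitions are in Section III, Clinical Outcomes; the control source is in Section III, Research Design and Methods.

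| Event | Criterion named | Source assigned to controls | Link between the two stated? |
|---|---|---|---|
| Stroke/TIA, coma, MI, ventilation, reoperation, thrombosis | STS | STS Database | Criterion and source match by name |
| Acute kidney injury | RIFLE | STS Database | No |
| Surgical-site infection | NHSN | STS Database | No |
| Low-output failure | Cited cohort study | STS Database | No |

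No section says that control charts will be reviewed against the three non-STS criteria, or that treated patients will be counted by their STS codes instead.

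**2. Size: inputs.** The plan has no power or event-rate figure to reproduce; the Biostatistics section says no formal power calculation was done. From the documents: 25 patients per group, chi-square or Fisher's exact test for dichotomous variables, significance at P < .05. Assumed: a two-sided test (sidedness is not stated), no true drug effect, and the rate that each group's counting rule would flag.

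**3. Formula.** Let p1 and p2 be the flagged rates under the two rules.

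- Spurious difference = p1 − p2; expected counts = 25·p1 and 25·p2.
- Probability of p<0.05 = sum, over all a, b = 0,…,25 for which Fisher's two-sided p for a/25 v b/25 is below 0.05, of Bin(a; 25, p1) × Bin(b; 25, p2).

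**4. Results.**

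| Assumed rates | Expected counts | Spurious difference | Fisher p<0.05 |
|---|---|---|---|
| 10% v 5% | 2.5 v 1.25 | 5 points | 1.3% |
| 20% v 15% | 5 v 3.75 | 5 points | 3.5% |
| 20% v 10% | 5 v 2.5 | 10 points | 8.6% |
| 30% v 15% | 7.5 v 3.75 | 15 points | 15.0% |
| 30% v 10% | 7.5 v 2.5 | 20 points | 30.5% |
| 30% v 5% | 7.5 v 1.25 | 25 points | 54.9% |

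With one shared rule the same calculation gives 0.9% at 10%, 2.2% at 20% and 2.3% at 30%.

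**5. Direction.** The groups are equal in size, so the table is unchanged if p1 and p2 are swapped. If the rule used for treated patients is the broader one, the treatment looks harmful; if the narrower, it looks protective. The documents do not say which applies.

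**The case against.** The strongest reply is that the protocol sets one definition per event. Clinical Outcomes does not limit its criteria to treated patients, and the third secondary outcome refers to pre-defined events in each group. A reader might infer from the control source that controls will in fact be coded by different rules. The documents do not support that: a data source is not a definition, and no section prescribes a second rule for controls.

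Nor can it be shown that the registry is unable to supply these events. Its fields are not described. It is called institutional, Section VIII lists EPIC without restricting it to treated patients, and Table 1 shows creatinine as standard of care. RIFLE could therefore probably be derived for controls from their charts, if these come from the same hospital.

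Aim 5 is also secondary. The primary objective is enrollment and adherence, and the Biostatistics section calls the analysis mainly descriptive and any test results preliminary. A Fisher rejection rate is therefore a poor main measure of harm, and with uncommon events or a mild mismatch it hardly moves.

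Most of this stands. It removes the claim that a mismatch is certain and any claim about its direction. What remains is that the one sentence assigning a source to controls names the registry alone, and nothing joins the three non-STS criteria to it. That a common method is feasible does not make it planned. A descriptive estimate is biased by unequal counting just as a test is, and this one is meant to inform a later trial.

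**Conclusion.** The concern holds in a limited form. As written, the plan does not ensure a common source and a common rule for the renal, infection and low-output events of Aim 5. The main harm is a biased rate difference in a secondary, descriptive aim that feeds the randomized trial's design.

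Under the assumed rates, the spurious difference is 5 to 25 percentage points and the chance of p<0.05 without a drug effect runs from 1.3% to 54.9%. The upper end needs a common event of which one rule catches only a sixth (30% v 5%). If one rule catches half of what the other does, the figures are 1.3% to 15.0%. All of these rates are assumptions, and none is specific to infection or low-output failure.

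The documents do not establish that the treatment would look harmful, or that the two groups will certainly be coded differently. The STS-defined events are not affected by this definitional gap, and neither is the primary feasibility objective.

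**What to change.** For each Aim 5 event, state one source and one definition that apply to both groups. Two routes are open:

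- **STS-coded field** for treated patients and controls alike, wherever the registry has a field for the event.
- **The criterion already named in Clinical Outcomes**, abstracted from EPIC in both groups with the same form and the same follow-up window. For example, derive RIFLE from standard-of-care creatinine in both groups and leave out the research-only samples, so that treated patients are not tested more often. Assessors should preferably be blind to group.

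Where an event cannot be obtained in the same way for controls, report it for treated patients only, with its confidence interval and no between-group comparison.

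The cost is a few lines in Section III and the Biostatistics section and, on the second route, abstraction of 25 control charts alongside the 25 treated ones. The first route needs no control chart review but may yield fewer coded events, and it would replace the RIFLE, NHSN and low-output criteria in the comparison. Those criteria could still be reported for treated patients.
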